5.5.2.2 Participant suspended by the investigator of the Study

The investigator and the designated team may use their medical judgment to terminate a participant's enrollment in the study if they determine that the participant's continued participation in the study could result in safety risks to the participant. The investigator must immediately inform the study's medical monitor of plans for the early withdrawal of a participant from the study. Participants withdrawn by the investigators will also have the opportunity to consent to the three options described above. All participants withdrawn early from the study for any reason must complete the Early Study Termination procedures described and be monitored for safety after receiving the last dose of study medication. Randomized participants who are withdrawn from the study for any reason will not be replaced.

5.5.2.3 Participants with early discontinuation

For all participants who drop out or discontinue the study prematurely (including participants who withdraw their consent), survival information may be verified through a search of a public database at the end of the study.

6. STUDY TREATMENTS

6.1 *Treatment blinding*

To minimize the potential for bias during the treatment phase, treatment randomization information will be kept confidential by a non-blinded biostatistician and will not be disclosed to third parties until the study database is finalized for statistical analysis upon completion of recruitment and follow-up of the last scheduled patient. The study is blinded, and neither the patient nor the investigator, the research team, nor existing committees will have access to the contents of the vials, which are produced sealed and hermetically closed. Similarly, the sponsor and the designated person will not have access to the randomization data. Treatment vials will be distributed using codes maintained by an unblinded biostatistician not involved in the research. The Data Monitoring Committee (DMC) and the drug safety team will not have access to participant allocation during the

interim assessments planned in the study, except in foreseeable situations (decision to discontinue any arm of the study, whether due to efficacy or futility, termination of the study, or for reasons of overall participant safety).

The clinical trial supply management team will have access to general information on investigational products at the site level for the management of packaging and distribution activities, as well as for the supervision of investigational product inventory levels in drug warehouses and at study sites, but will not have access to the allocation codes for these products.

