4 RESEARCH PLAN

4.1 Study Design

The study consists of an in-person screening and randomization visit, which will occur simultaneously, and visits conducted via in-person visits, telephone contact, and social media applications using video conferencing. The following visit schedule will be implemented for the metformin and corresponding placebo arms (adjusted for treatment days according to the intervention arms):

- V1 (Day 1) - Screening, Baseline, Randomization (Start of treatment phase)
- V2 (Day 7) - Follow-up Visit / Tolerance to Investigational Medicinal Products
- V3 (Day 30) - Follow-up visit
- V4 (Day 60) - Follow-up visit (in-person visit recommended)
- V5 (Day 90) - Follow-up visit after completion of the investigational product
- V6 (Day 180) - Follow-up visit after completion of the investigational product

The D90 and D180 visits are considered post-study visits. The objective of these visits is to evaluate late effects of the investigational medical products and the persistence of any therapeutic effect observed during the treatment phase. This phase is an open-label, post-study phase.

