10.8.3 Exposure during pregnancy and birth events

10.8.3.1 Definition of exposure during pregnancy and birth events

Decades of experience with metformin use suggest that this medication should not be prescribed to pregnant participants without a careful assessment of the risks and benefits of its use during this phase. Thus, pregnancy is not expected during the treatment phase, and women must use contraceptive methods to prevent pregnancy (if necessary, we will provide an effective contraceptive method for use during the medication period).

When a female participant becomes pregnant during the study and has received study treatment, the pregnancy outcome must be monitored, and the safety of the mother and fetus must be assessed. Therefore, the outcome of all such pregnancies (including normal births) must be monitored and documented, even if the participant has been withdrawn from the study or the study has been terminated.

A female participant must immediately inform the investigator if she becomes pregnant during the study. The investigator must counsel the participant and discuss the risks and benefits of continuing the study medication and advise the patient on follow-up until the child is born.

The investigator is responsible for monitoring the participant and the pregnancy outcome and for reporting this information to the sponsor. Every effort should be made to collect information on the pregnancy outcome up to 90 days after delivery (or otherwise, as appropriate).

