16 PROCEDURES FOR PROTOCOL AMENDMENTS OR EARLY TERMINATION OF THE STUDY

16.1 Protocol Deviation

The investigator must not perform unplanned procedures or deviate from the protocol without prior written approval, except in medical emergencies. In the event of a medical emergency, the investigator must notify the medical monitor as soon as possible. Any other changes to the protocol must be implemented as an amendment to the protocol. The criteria for describing protocol deviations and how they will be handled will be documented in the study manual.

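### Section 6.1 withholds allocation until the database is final and states no individual code break, although a few safety decisions during treatment depend on which product was taken

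*Protocol*

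**What the plan says.** Section 6.1 leaves the randomization information with a biostatistician, to whom it assigns no clinical role: "Treatment vials will be distributed using codes maintained by an unblinded biostatistician not involved in the research". Release comes only at the end: the information "will not be disclosed to third parties until the study database is finalized for statistical analysis upon completion of recruitment". The parties kept out are listed one by one. For the clinical side and the committees, "neither the patient nor the investigator, the research team, nor existing committees will have access to the contents of the vials"; for the sponsor, "the sponsor and the designated person will not have access to the randomization data". The supply team also lacks the codes.

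The DMC and drug safety team are blinded at the planned interim assessments "except in foreseeable situations (decision to discontinue any arm of the study". The remaining examples in that exception are termination of the study and the safety of participants overall. The protocol overview likewise foresees unblinding by arm, through the DMC.

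Two other places touch on the subject. Section 16.1, on deviations, says: "In the event of a medical emergency, the investigator must notify the medical monitor as soon as possible". Section 4.1 says of the visits at days 90 and 180: "This phase is an open-label, post-study phase".

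**The concern.** In a double-blind drug trial, the treating physician normally needs a way to learn one participant's allocation when that knowledge changes care. Here the text does more than leave the procedure out. It denies access to every party who might use it, and its exception is written for decisions about arms or the whole study.

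The protocol also imposes duties that can turn on product identity. Section 10.8.3.1 requires the investigator to discuss with a pregnant participant the risks and benefits of continuing. The only drug-specific pregnancy advice there concerns metformin, of which it says that "this medication should not be prescribed to pregnant participants without a careful assessment of the risks and benefits of its use". Sections 10.6.1, 10.6.2 and 10.7.3 judge whether a reaction is unexpected against the registered information for the drug concerned. They make the sponsor or investigator responsible for notifying SUSARs, and section 6.1 blinds both. What is at stake is the safety of individual participants and the correct classification of a small number of reports.

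**Working it through.** The protocol gives no figure to reproduce, so the check sets its sections side by side.

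**1. Is there a route to one participant's code during treatment?**

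| Section | What it provides | Access to the code? |
|---|---|---|
| 5.5.1, 6.7.1 | Participant or investigator may stop the product | No |
| 5.5.2.2 | Investigator may withdraw a participant and informs the medical monitor | No |
| 8.4 | Unscheduled visits | No |
| 10.7.2 | SAE report within 24 hours | No |
| 10.7.3 | Duty to notify SUSARs | No |
| 10.8.1, 10.8.2 | Overdose, interactions and other special situations | No |
| 10.8.3 | Pregnancy counselling, reporting and newborn follow-up | No |
| 16.1 | Emergency deviations, notice to the medical monitor | No |
| 4.1 | Open-label phase at days 90 and 180 | After dosing ends; no release of codes described |

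**2. When does identity matter?** That depends partly on whether tablets are matched across the two drugs, and the protocol points both ways.

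- Towards a separate placebo for each drug: the research flowchart gives each arm a placebo of the same formulation and dosing. The diabetes exclusion (5.3, item 5) names a metformin placebo arm. Section 4.1 pairs metformin with its own placebo, section 6.8.1 lists prohibited drugs by arm, and section 12.2 provides a placebo for each active arm.
- Towards products that cannot be told apart: identical bottles (6.4) and kits from which nobody can identify the study drug (4.1.2).

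With separate placebos, the investigator may know which drug is in question and lack only active versus placebo. With full matching, all three allocations remain open. In both cases it is unknown whether the participant took active drug.

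**3. Consequence by type of case.**

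- *Pregnancy.* Stopping is possible at once. What stays unknown is whether mother and fetus were exposed to active drug and, if tablets are matched, to which one.
- *Emergency or overdose.* The code matters when management differs by product.
- *Potential SUSAR.* Take a serious event judged related:
  - Listed for neither drug: unexpected for both. The code is needed only to separate active from placebo.
  - Listed for both drugs: expected for both. The code does not change expectedness.
  - Listed for one drug only: expectedness depends on which drug was taken. The protocol's own lists illustrate this: QT prolongation appears for fluvoxamine (7.2.1) and not for metformin (7.2.2). Those lists are not the registered dossiers, so this is an illustration only.

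**4. The SAE definition.** Section 10.7.1 lists, among situations that are not SAEs, reactions expected for the study drugs under their registered dossier. A serious expected reaction therefore drops out of SAE reporting. If it is expected for one drug only, SAE status depends on an allocation that nobody at the site may know. This sits badly with section 10.7.2, which wants all SAEs reported whatever their relationship to treatment.

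**5. Coverage.** 3 arms × 500 = 1,500 participants are under the rule. The number with a qualifying event is not given. Section 10.7.3 expects no SUSARs, and pregnancy is tested for at entry, with contraception required.

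**The case against.** The best reply is that the practical harm is small. The product can be stopped without the code (5.5.1, 6.7.1). SAEs go out within 24 hours regardless of relationship (10.7.2), and a missing causality assessment counts as related (10.4.2), so the first report does not wait for unblinding. Pregnancy is excluded at entry, and counselling can proceed as if active drug had been taken. All of this stands, and it limits the point to a few cases. It does not tell anyone what a fetus was exposed to, or settle expectedness where the drugs' listings differ.

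A second reply is that the procedure may sit elsewhere. Section 16.1 mentions a study manual, 11.1 a DMC charter and 10.7.2 a safety contact sheet, none of them shown. The finding is therefore that the protocol states no route, not that none exists anywhere. But a manual that gave the investigator access would contradict section 6.1 as written.

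A third is that the drug safety team already has a safety-based exception. It does, but the wording ties it to interim assessments and overall safety, and it gives the treating investigator nothing.

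A reader might also infer more than the text supports:

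- *That the investigator can never tell which of the three products is involved.* Several sections point to drug-specific placebos, so only active versus placebo may be hidden.
- *That SUSAR reporting as a whole fails.* The problem is confined to the situations in step 3 of the working.
- *That a probability of active exposure can be quoted.* With drug-specific placebos it would depend on how the 500 placebo participants are divided, which the protocol does not give.

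**Conclusion.** The point holds in limited form. Section 6.1, read as written, denies the investigator and sponsor any access to an individual allocation until the database is final, and nothing else in the protocol opens a route during treatment. The consequence falls on the few participants with a pregnancy, an emergency or overdose, or a potential SUSAR for which identity decides something. Their number cannot be derived from the document. Efficacy estimates and power are unaffected.

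The conclusion rests on the protocol alone and does not depend on how the placebos are matched; matching changes only how much is unknown. The 10.7.1 exclusion is a separate defect that stands on its own. The amendment should be made because it protects individual participants at little cost. It is not a threat to the validity of the trial.

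**What to change.** Add a paragraph to section 6.1:

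- An individual emergency code break for the investigator, through the existing IWRS and available at any time, limited to cases where product identity affects the participant's care. Each use is logged with date, reason and requester.
- Case-level unblinding for potential SUSARs, confined to the drug safety function.
- Staff who collect the FSS, the committees and the blinded statisticians stay blinded. The participant, who rates the FSS personally, is told only if clinically necessary.
- Unblinded participants remain in the intention-to-treat analysis.

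Cross-refer to this paragraph from 10.7.3, 10.8.3 and 16.1. Separately, delete the line in 10.7.1 that takes dossier-expected reactions out of the SAE definition.

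The cost is an IWRS function, one paragraph with cross-references and one deleted line. The downside is a few logged unblindings and some additional SAE reports.

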6.2 Dosage Form/Administration

Metformin will be provided to the participant in the form of 500 mg extended-release tablets for oral use.

Fluvoxamine will be provided to the participant in the form of 100 mg tablets for oral use.

6.3 Dosage and administration

Participants assigned to the 500 mg extended-release metformin treatment group should take the medication every 12 hours for 60 days.

Participants assigned to the 100 mg dose of fluvoxamine should take the medication every 12 hours for 60 days.

6.4 Supply of the investigational medicinal product

The investigational products will be provided to the participant at no cost, with instructions for use solely for the purpose of the research. Bottles of identical format will be provided, containing sufficient medication for use as scheduled. The patient must return the blister packs for accounting of the medications delivered.

The medications used in the study will come from pharmaceutical manufacturers with commercial authorization for their production, already approved by ANVISA, or through imports authorized by ANVISA for specific use in this research protocol.

6.5 Study Treatment Allocation

Each eligible participant will be assigned to one of three treatment groups via an Internet-based remote randomization system (IWRS), namely: metformin, fluvoxamine, or the corresponding placebo.

After enrollment in the initial phase of the study, each participant will receive instructions on the appropriate dosage of the medications and individualized instructions on when to take them and other concomitant medications, after considering the participant's current medication regimen. The participant will be instructed to follow the agreed-upon dosing instructions for the remainder of the study to encourage adherence. The investigator will determine whether the study medication administration instructions need to be changed at each scheduled telephone follow-up visit, and any changes will be communicated to the participant.

Participants who qualify for the treatment phase will be randomized to receive the study products as allocated to one of the study arms.

Participants will also be instructed to keep their empty/unused medication bottles, which will be collected by the research team on Day 60 for assessment of compliance during the treatment phase. Participants will be instructed to return empty/unused medication blister packs in the containers in which they were originally provided.

Adherence will be documented. Adherence will be assessed based on the number of prescribed medications, the duration of treatment, and the quantity of dispensed and returned medications (used and unused). Adherence as reported by the study participant will also be considered.

Treatment adherence will be considered satisfactory if the participant has taken 80% of the prescribed dose for the study period.

6.6 Delivery , storage, and accounting by the research center

6.6.1 Delivery by the study site

Once the study site has been approved to receive the study drug, it will receive an initial shipment of investigational medicinal products sufficient to treat 20 participants. The need for replenishment of the study drug will be assessed regularly, taking into account the number of enrolled participants, the number of participants currently being treated at the study site, and overall study participation.

6.6.2 Storage

The pharmacist or their representative will verify and confirm receipt of each shipment of medication. The medications will be shipped and stored at room temperature not exceeding 30°C and away from direct sunlight. All study medications will be stored in a secure location. No participants other than those included in this specific clinical trial should take the medications provided for this study. The medication provided for this study must not be used in any animal or laboratory research.

6.6.3 Accounting

All investigational products dispensed to participants must be accurately recorded in the investigational product inventory maintained at the study site by the study pharmacist or qualified representative. Participants must be instructed to return all investigational products dispensed to them (blister packs and containers, whether used or unused), which will be collected by the research team during follow-up visits. All used investigational product blister packs and containers will be retained on-site by the study pharmacist or qualified representative for verification by the study monitor. Verification of inventory and adherence to the investigational product for all investigations will be performed by the study pharmacist or qualified representative at each scheduled study visit.

6.7 Change in medication dose

6.7.1 Adverse reactions during use of investigational products

The study participant must contact the study team if they experience any adverse reaction they believe is associated with the investigational product. Similarly, the patient will be monitored daily via safety phone calls to check for the presence of unwanted symptoms, adverse reactions, and other signs or symptoms that may be present. The participant may be scheduled for an additional safety visit whenever the investigator deems it necessary, based on the information obtained during the telephone contact.

The decision to temporarily discontinue the medication may be made at any time by the patient or the investigator. An attempt should be made to resume the investigational products whenever possible.

6.7.2 Standard of Care

During the treatment phase, all participants will receive standard of care in accordance with the recommendations of the guidelines.

6.8 Prohibited therapy, special considerations, and concomitant treatment

6.8.1 Prohibited medications

During the study, the following medications will be prohibited while the patient is being treated with the study medications:

Fluvoxamine Arm: Selective serotonin reuptake inhibitors (except sertraline)

1. Metformin Arm: Metformin

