5.3 Exclusion Criteria

Participants who meet any of the following criteria will not be eligible to participate in the study:

1. Known acute SARS-CoV-2 infection;
2. Inability to understand the content of the Informed Consent Form or to follow the study procedures;
3. Known prior diagnosis of myalgic encephalomyelitis/chronic fatigue syndrome, unrelated to SARS-CoV-2 infection;
4. Known pre-existing dysautonomia, unrelated to SARS-CoV-2 infection;
5. Diabetes mellitus (exclusion criterion for the Metformin and Metformin Placebo arms);
6. Known history of creatinine clearance below 30 ml/min or on dialysis;
7. Known stroke within the 3 months prior to screening;
8. Known severe anemia, defined as < 8 g/dL;
9. Body Mass Index (BMI) > 40 .
10. Known diagnosis of Lyme disease;
11. Any use of illicit drugs other than marijuana within 30 days prior to informed consent;
12. Pregnant women or women of childbearing age who do not agree to use an effective method of contraception for 90 days from the date of signing this consent form;
13. Women who are breastfeeding;
14. Expected hospitalization for elective surgical procedures lasting more than 48 hours;
15. Contraindications for the METFORMIN arm
 - a. Participants currently taking metformin;
 - b. Participants with creatinine clearance < 30 ml/min, a history of KIDIGO IV, or currently undergoing dialysis.
16. Contraindications for the FLUVOXAMINE arm
 - a. Use of serotonin reuptake inhibitors (donepezil, fluoxetine, escitalopram, paroxetine);
17. Current severe comorbid psychiatric disorder (e.g., clinical depression, anxiety, sleep disorder, eating disorder, substance abuse) that is uncontrolled and associated with significant symptoms or requiring the use of a medication contraindicated in this study;
18. Clinical history of moderate to severe hepatic impairment or hepatic cirrhosis with a Child-Pugh score of C or higher;
19. A clinical history of severe chronic lung disease with significant limitation of activities;
20. Inability of the participant to provide informed consent or adhere to the procedures proposed in the study;
21. Taking medications known to cause chronic fatigue as a side effect (except for participants with chronic cardiovascular disease who are on chronic beta-blocker therapy);
22. Known hypersensitivity and/or intolerance to fluvoxamine or metformin;

23. Any clinical condition that, in the investigator's opinion, may preclude participation in this study.

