6.8.2 Concomitant medications

Information regarding concomitant medications (prescription medications, over-the-counter medications, herbal and naturopathic medications, etc.) will be collected at the start of screening and at each follow-up visit.

In general, participants should continue with the same medications and regimens they were taking at the time of study enrollment. The doses of these concomitant medications should be kept as stable as possible during the study. In general, medications that the investigator considers appropriate for the treatment of any intercurrent illness or preexisting condition that is not on the list of prohibited medications or that does not constitute an exclusion criterion for participation in this study will be permitted.

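### The entry rule and the on-treatment rule for serotonin reuptake inhibitors disagree, and the on-treatment rule is written by arm, so blinded sites cannot apply it as it stands

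*Protocol*

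**What the plan says.** Item 16 of the exclusion criteria (section 5.3, repeated in the Protocol Overview) is headed "Contraindications for the FLUVOXAMINE arm". Its one entry is "Use of serotonin reuptake inhibitors (donepezil, fluoxetine, escitalopram, paroxetine". The list that contains it opens study-wide: "Participants who meet any of the following criteria will not be eligible to participate in the study".

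For the treatment period, section 6.8.1 has two lines. One, labelled for the fluvoxamine arm, prohibits "Selective serotonin reuptake inhibitors (except sertraline" and the other reads "Metformin Arm: Metformin". Placebo has no line.

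Section 6.8.2 says that, in general, "participants should continue with the same medications and regimens they were taking at the time of study enrollment". It then describes which other treatments are allowed by pointing to both the prohibited list and the exclusion criteria.

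On blinding, section 6.1 states that "neither the patient nor the investigator, the research team, nor existing committees will have access to the contents of the vials". Section 4.1.2 has all exclusions cleared before participants are randomised 1:1:1.

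**The concern.** Two questions arise. The first is whether the entry list and the on-treatment list describe the same set of drugs. If they do not, a site may enrol someone whose existing medicine becomes prohibited, or turn away someone whose medicine would have been allowed.

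The second is whether a rule that names an arm can work when the people who must apply it do not know the arm. The primary outcome is a fatigue questionnaire completed by the participant (section 9.4), so the blind carries much of the protection against bias. Fluvoxamine is itself a member of the restricted class (section 1.14), and metformin is a study drug. A rule that restricts each in one arm only touches the contrast being tested as well as the safety of those on fluvoxamine.

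**Working it through.** There is no figure to reproduce. The check sets the sections side by side.

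**Step 1: compare the two lists.** The bracket in exclusion 16a can be read as examples (reading A) or as the full list (reading B).

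| Drug | Entry, reading A | Entry, reading B | On treatment, fluvoxamine arm (6.8.1) |
|---|---|---|---|
| Any of the four named, classed as the protocol classes them | barred | barred | prohibited |
| Sertraline | barred | not barred | excepted |
| Another SSRI, neither named nor sertraline | barred | not barred | prohibited |

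Under A the rows disagree for sertraline. Under B they disagree for the other SSRIs. Neither reading makes the two rules agree.

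**Step 2: see whether section 6.8.2 settles it.** It does not. Its general rule is to carry on baseline medication. Its permission clause joins the prohibited list and the exclusion criteria with the word *or*, so a drug that appears on only one of them can be read as permitted. Exclusion 17 refers to medication contraindicated in the study, which depends on the same unsettled lists.

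**Step 3: see who can apply section 6.8.1.** Given the blinding in section 6.1, a site has three courses:

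- learn the allocation and apply the matching line, which breaks the blind;
- leave the line unapplied, so a stated restriction does not reach those on fluvoxamine;
- apply both lines to everyone, which no section says.

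**Step 4: follow section 6.8.1 literally by arm.**

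| Arm | Restricted during treatment |
|---|---|
| Fluvoxamine | SSRIs other than sertraline |
| Metformin | metformin |
| Placebo | nothing listed |

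The permitted co-medication differs between each active arm and placebo. Where the protocol wants a rule to reach placebo it can say so: exclusion 5 (diabetes) names the metformin placebo as well. Section 6.8.1 does not.

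**Step 5: take out what entry screening already removes.** The opening of the exclusion list and the order of events in section 4.1.2 allow items 15 and 16 to be applied to every candidate before randomisation, despite their arm headings. Then current metformin users and users of the four named drugs never reach any arm. What remains is mainly the drugs on which the lists differ (Step 1) and drugs first started during the 60 days. The second group is foreseeable: section 7.1 may admit people with controlled depression or other psychiatric conditions, and section 6.8.2 lets the investigator treat intercurrent illness.

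**The case against.** The strongest reply is that entry is study-wide. Anyone meeting any exclusion is out of the trial, sections 4.1.2 and 5.4 require this before randomisation, and exclusion 17 removes further people with no arm limit. This stands, and it removes most of the imbalance at baseline. It does not reach section 6.8.1, which governs what happens after allocation, and it leaves the mismatch in Step 1 untouched.

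A second reply is that the introduction to section 6.8.1 speaks generally of patients on study medication, so the arm labels may only give the reason for each line and sites may apply both to everyone. That is possible, and it means unblinding is not a necessary result. But the text does not say it, and a site would have to guess.

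A third reply is that section 6.8.2 is only a general rule and refers back to the prohibited list. This is fair: it does not flatly tell anyone to continue a prohibited drug. It also does not say which list governs when they differ.

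Two stronger inferences are tempting and are not supported:

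- A reader might infer from section 1.14.7 that SSRI use in the other arms would dilute the treatment effect. The 26% reduction reported there concerns only SSRIs with S1R agonist activity, and the outcome was the incidence of Long COVID, not improvement of established fatigue.
- A reader might assume that 5% to 10% of participants use such drugs and put 25 to 50 of each arm of 500 under conflicting rules (0.05 × 500 = 25; 0.10 × 500 = 50). The rate is not in the document, it would cover all users and not just those on whom the lists differ, and the on-treatment line names only one arm.

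**Conclusion.** The point holds as an inconsistency of drafting with consequences for conduct. The entry and on-treatment rules disagree under either reading of the bracket, and section 6.8.1 cannot be carried out as written by staff who are blinded.

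The consequences are possibilities, not certainties: differing co-medication by arm, a local break of the blind, or a restriction that goes unapplied. They are limited mainly to drugs on which the lists differ and drugs started after randomisation, provided sites apply the exclusions to all candidates. The document gives no rate of SSRI or metformin co-medication, so neither the number of participants affected nor any bias in the fatigue score can be computed. Nothing here shows that the primary comparison is compromised. It is worth correcting because it bears on both safety and the blind, and because the correction is cheap.

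**What to change.** The sponsor should reconcile item 16 in the Protocol Overview and section 5.3 with sections 6.8.1 and 6.8.2, so that the entry list and the on-treatment list agree. The text should make clear whether the bracketed names are examples or the whole list. Section 6.8.1 should be restated in a form that blinded sites can apply without knowing the allocation, and section 6.8.2 should say which list governs. Which drugs belong on the list is a clinical matter for the sponsor, and no view is taken on it.

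The cost is a wording amendment with the approvals set out in section 16.2 and a notice to sites. Sample size and analysis do not change. Depending on how the lists are reconciled, a small number of otherwise eligible people may be excluded. Concomitant medication is already recorded at screening and at each follow-up visit, so the sponsor could count, without unblinding, how many participants take a drug on which the lists differ.
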